6.3.3. Dose Proportionality Analysis

Dose proportionality will be assessed using log-transformed PK parameters, AUC_{0-t} at steady state and C_{max} , and a linear regression approach to log-transformed dose levels. The power model will be used to analyze the dose proportionality. The estimate of the ratio of the dose normalized geometric means, R_{dnm} , and the corresponding 90% CI will be derived.

The power model is defined as follows:

$$\log(PK_i) = \alpha + (\beta) * \log(\text{dose}_i) + \mathcal{E}_i$$

Where

PK_i is the PK parameter (C_{max} or AUC_{0-t} at steady state) observation for the subject i .

α is the population intercept.

β is the population slope.

$dose_i$ is the dosage for the subject i .

\mathcal{E}_i is the random error; $\mathcal{E}_i \sim N(0, \sigma^2_{\mathcal{E}})$ and independent.

The assumption for the power model is that the underlying relationship between log(PK parameter) and log(dose) is linear. The dose proportionality corresponds to the ratio of dose normalized geometric means (R_{dnm}), which is defined as ratio of the predicted geometric mean of the highest dose relative to the predicted geometric mean of the lowest dose. The dose proportionality would be declared when the 90% CI for the R_{dnm} falls entirely within the limit of 0.8 to 1.25.

Log(PK parameter) and log(dose) will be plotted in a line plot for AUC_{0-t} at steady state and C_{max} .

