
As the investigators entered repeated vital signs measurements differently, a decision was made to allow unscheduled visits data to be included in analysis.
	
Section 6.1.3 Handling of Multiple Observations or Out of Window Observations
 
None
	
A new paragraph has been added:
 
For vital signs data, if measurements are duplicated within the visit window, the data from the unscheduled visit will be used and the average of the scheduled and unscheduled visits will be taken for summary table. A footnote will be added to table to highlight the exception.

List of Abbreviations

ADAbs	Anti-drug antibodies
AE	Adverse event
ANOVA	Analysis of Variance
anti-PEG	Anti-polyethylene glycol
ATC	Anatomic therapeutic chemistry
AUC	Area under the curve
BLQ	Below limit of quantitation
BMI	Body mass index
Cl _s	Confidence Intervals
CL/F	Apparent clearance
C _{max}	Max concentration
CRF	Case Report Form
CSR	Clinical study report
C _{trough}	Trough concentration
CV	Coefficient of variation
DLT	Dose limiting toxicity
DMC	Data monitoring committee
DRM	Data Review Meeting
ECG	Electrocardiogram
EDC	Electronic data capture
FFAs	Free fatty acids
FGF 21	Fibroblast growth factor 21
FPG	Fasting plasma glucose
GIP	Gastric inhibitory polypeptide
GLP-1	Glucagon-like peptide - 1
HbA1c	Hemoglobin A1c
HDL	High density lipid
HOMA-B	Homeostatic Model Assessment for β Cell Function
HOMA-IR	Homeostatic Model Assessment for Insulin Resistance
hs-CRP	High sensitivity c-reactive protein
IP	Investigational product
IRB	Investigational Review Board
IV	Intravenous
K _{el}	Terminal elimination rate constant
LDL	Low density lipid
LS	Least Squares
MAD	Multiple ascending dose
max	Maximum
MedDRA	Medical dictionary for regulatory affairs

HM-GCG-102 Statistical Analysis Plan

min	Minimum
MRI	Magnetic resonance imaging
MRI-PDFF	Magnetic resonance imaging – proton density fat fraction
n	Sample size
nAbs	Neutralizing antibodies
PD	Pharmacodynamics, pharmacodynamic
PK	Pharmacokinetics, pharmacokinetic
PT	Preferred Term
QTcF	Frederica's QT corrected interval
R _{dnm}	Ratio of dose normalized geometric means
SAE	Serious adverse event
SC	Subcutaneous
SD	Standard deviation
SE	Standard Error
SMBG	Self-monitoring of blood glucose
SOC	System organ class
TEAE	Treatment-emergent adverse event
T _{max}	Time to max concentration
TSH	Thyroid stimulating hormone
T2DM	Type 2 diabetes mellitus
VLDL	Very low density lipid
VS	Vital signs
Vz/F	Apparent volume of distribution

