WHO DDE	World health organization drug dictionary
WHR	Waist hip ratio

1. Introduction

This document describes the statistical methods and data presentation in the analysis and summary of the safety, tolerability, pharmacokinetics (PK) and pharmacodynamics (PD) of HM15136 in obese or overweight subjects with comorbidities. The original statistical analysis plan (SAP) was developed based on Hanmi Pharmaceutical Protocol HM-GCG-102 (version 5.0 dated 20 MAY 2020) and case report form version 5.0 dated 11 JUNE 2020 for Part 2 Study and 6.0 dated 6 JULY 2020 for Part 1 Study.

The original SAP was finalized prior to data analyses and before database lock of Part 1 Study. The current SAP amendment is created to incorporate contents from protocol version 6.0 (dated 29 OCTOBER 2020, post Part 1 database lock) regarding the change of time point for dose escalation from Cohort 5 to Cohort 6 and additional Data Review Meeting (DRM). The conduct of Cohorts 6 and 7 is determined to be optional for Part 2 Study.

Any major differences between the statistical methods provided in the clinical study protocol and this SAP will be explained herein. Any major changes and deviations from this SAP to the final data analysis must be substantiated by sound statistical rationale and fully documented in the final clinical study report (CSR).

2. Study Overview

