The dose of Cohorts 3 and 4 can be adjusted, but may not be over the planned dose of 0.08 mg/kg. The escalated dose should not be more than 2 times over the dose of the previous cohort.

In Part 2, after the review of the safety data, obtained by the 9th subject's visit on Day 29 of Cohort 3 (in Part 1), Cohort 4 can proceed with a dose of ≤ 0.08 mg/kg dose, which is the planned maximum dose.

A DMC will assess the safety and will make dosing and cohort escalation assessments and recommendations for the study progress of Part 2. After the review of the safety data in Part 1, Part 2 may or may not proceed. Cohort 4 may be conducted with a lower number of subjects. Cohort 5 may start immediately and may overlap with the conduct of subjects in Cohort 4.

In Part 2, dose escalation from Cohort 5 to the subsequent Cohort 6 will be made after a DRM, held by Sponsor, Investigator and Medical Monitor, and the safety data obtained from the 9th subject's visit on Day 43 (=after 6 weeks of dosing) will be reviewed. Per DRM of Cohort 5 (after the 9th subject's visit on day 43 of Cohorts 5), a dose escalation to Cohort 6 will not proceed and another DRM will be held after all 12 subjects in Cohort 5 have completed the final study visit on Day 113 (=F/U Visit), in order to assess the safety data.

Dose escalation from Cohort 6 to the subsequent Cohort 7 will follow the same dose escalation scheme and DRM(s) of the previous cohort.

Cohorts 6 and Cohort 7 may be conducted at doses of 0.04 mg/kg and at 0.06 mg/kg respectively upon approval by the Investigator, Medical Monitor, and the Sponsor, if the safety is demonstrated in Cohort 5. If sufficient safety data are collected after cohort 5 or cohort 6 have been completed, no additional cohorts will be conducted, and sponsor may choose to complete study.

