2.2. Randomization and Blinding Procedures

The subjects enrolled in this study would be assigned randomly to each treatment group. Subjects in Part 1 will be assigned to HM15136 and placebo in a 3:1 ratio, in the case of Part 2, up to 66 subjects will be assigned to HM15136 and placebo. Thirty subjects in Cohort 4 will be

HM-GCG-102 Statistical Analysis Plan

assigned to HM15136 and placebo in a ratio of 1:1, and 12 subjects in Cohorts 5 to 7 will be assigned to HM15136 and placebo in a 3:1 ratio according to rules below in Table 1.

Table 1. Treatment Assignment

Part	Cohort	Treatment Assignment*	
Part 1	1	HM15136 0.02 mg/kg (N=9)	Placebo (N=3)
	2	HM15136 0.04 mg/kg (N=9)	Placebo (N=3)
	3	HM15136 \leq 0.08 mg/kg (N=9)	Placebo (N=3)
Part 2	4 (DM)	HM15136 0.06 mg/kg (N=15)	Placebo (N=15)
	5 (DM)	HM15136 \leq 0.02 mg/kg (N=9)	Placebo (N=3)
	6 (DM)	HM15136 \leq 0.04 mg/kg (N=9)	Placebo (N=3)
	7 (DM)	HM15136 \leq 0.06 mg/kg (N=9)	Placebo (N=3)

* In Part 1, dosage of Cohort 3 can be adjusted, but not be over the dosage presented in the table. The escalated dose should not be over twice the dose of the previous cohort.

* In Part 2, if necessary, after the review of the safety data obtained by the 9th subject's visit on Day 29 of Cohort 3 in Part 1, the Cohorts 4 to 7 can proceed within the doses in Table 1. The dose and study progress of Part 2 should be guided by the recommendations of the DMC. After the review of the safety data in Part 1, Part 2 may or may not proceed. The conduct of Cohorts 6 and 7 will be optional.

Due to COVID-19 outbreak, an interim analysis based on partially validated data for Part 1 will be performed for administrative purpose prior to database lock of Part 1. For this planned interim analysis, unblinding will occur after partially validated data transfer for Part 1. Designated personnel not involved in the study conduct will perform the interim analysis. Only authorized members who are listed in the Interim Analysis Unblinding and Information Dissemination Plan will have access to review the summary tables or figures of the interim analysis results, in which the information is presented in a grouped fashion with the actual treatment, e.g., mean treatment effect.

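### SAP 6.3.3 defines R_dnm without dividing by dose, so the 0.8–1.25 rule as written fails an exactly dose-proportional drug (ratio about 4 or 3 instead of 1)

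*SAP*

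**What the plan says.** SAP 6.3.3 fits a power model, log(PK) = α + β·log(dose) + error, to C_max and to AUC_0-t at steady state. It first introduces the summary statistic as "The estimate of the ratio of the dose normalized geometric means", and the List of Abbreviations expands R_dnm in the same way: "Ratio of dose normalized geometric means". Later in 6.3.3 the statistic is defined: "which is defined as ratio of the predicted geometric mean of the highest dose relative to the predicted geometric mean of the lowest dose". The decision rule follows directly: "The dose proportionality would be declared when the 90% CI" of R_dnm "falls entirely within the limit of 0.8 to 1.25".

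No formula for R_dnm appears in either document. SAP 6.3.2 log-transforms the PK parameters but does not divide them by dose. Protocol 11.2.7, item 10, gives only the regression of log parameter on log dose, with no R_dnm and no limits. Under SAP 6.1 the two parts are analysed separately, so each part has its own highest and lowest dose.

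**The concern.** The name and the definition describe different quantities. The name implies that each geometric mean is divided by its dose before the ratio is taken. The definition compares the undivided means. The modelled outcome is the raw PK parameter, so the predicted means are not already normalised.

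The limits make sense only for the dose-normalised quantity, which equals 1 under proportionality. Applied to the quantity as defined, the rule is turned round: a proportional drug fails, and a drug whose exposure does not change with dose can pass.

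PK is a primary objective (protocol 4.1). The protocol version that this SAP amendment incorporates is "dated 29 OCTOBER 2020, post Part 1 database lock", so a Part 1 result may already exist. SAP Section 7 states that the Part 1 interim covers all PK variables and supports planning of later studies, and that Part 1 results go into the final report with Part 2.

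**Working it through.** **Inputs.** Doses and active numbers are from SAP Table 1. In Part 1 they are 0.02, 0.04 and up to 0.08 mg/kg with 9 active subjects each. In Part 2, Cohort 4 has 0.06 mg/kg (15 active) and Cohort 5 up to 0.02 mg/kg (9 active); Cohorts 6 and 7 are optional. These are planning values: "In Part 1, dosage of Cohort 3 can be adjusted, but not be over the dosage presented in the table", and SAP 2.1 says "Cohort 4 may be conducted with a lower number of subjects". The documents give no between-subject CV, so 15–40% is assumed.

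**Step 1: the two quantities.** Let r be the ratio of highest to lowest dose. The predicted geometric mean at a dose is exp(α)·dose^β.
- As defined: R = r^β.
- As named: R = (GM_high/dose_high)/(GM_low/dose_low) = r^(β−1).

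**Step 2: exact proportionality (β = 1).**
- Part 1: r = 0.08/0.02 = 4, so R is 4 as defined and 1 as named.
- Part 2: r = 0.06/0.02 = 3, so R is 3 as defined and 1 as named.
- If Cohort 3 was dosed at 0.06 mg/kg, Part 1 also has r = 3.

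**Step 3: what the limits mean for β.** On the log scale the limits are ±ln 1.25 = ±0.223.
- As defined, R lies inside only for |β| < 0.223/ln 4 = 0.161 (r = 4) or |β| < 0.223/ln 3 = 0.203 (r = 3).
- As named, the windows are 0.839–1.161 and 0.797–1.203, centred on proportionality.

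**Step 4: interval width, Part 1.** Use σ = √ln(1 + CV²), SE(ln R) = ln(r)·σ/√Sxx and half-width = t(0.95, n−2)·SE. With 9 subjects at each of three doses spaced by a factor of 2, Sxx = 18·(ln 2)², so SE = 2σ/√18 = 0.471σ. With 25 degrees of freedom the half-widths are 0.120, 0.159, 0.198, 0.236 and 0.310 at CV 15, 20, 25, 30 and 40%.

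Typical 90% CI at β = 1:

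| CV | As defined | As named |
|---|---|---|
| 20% | 3.41–4.69 | 0.85–1.17 |
| 30% | 3.16–5.07 | 0.79–1.27 |

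**Step 5: chance of declaring proportionality.** This was obtained by numerical integration over the distribution of the residual variance. Part 1 and the Cohorts 4–5 flat case were also checked by simulation.
- Rule as defined, β = 1: below 10⁻¹⁰ in every design checked, at CV 15–40%.
- Rule as defined, flat exposure (β = 0):

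| Design | CV 15% | 20% | 25% | 30% | 40% |
|---|---|---|---|---|---|
| Part 1, Cohort 3 at 0.08 | 0.85 | 0.50 | 0.20 | 0.05 | 0.001 |
| Part 1, Cohort 3 at 0.06 | 0.860 | 0.520 | 0.210 | 0.054 | 0.002 |
| Part 2, Cohorts 4 and 5, 15 + 9 active | 0.927 | 0.655 | 0.342 | 0.128 | 0.009 |
| Part 2, Cohorts 4 and 5, 9 + 9 active | 0.84 | 0.48 | 0.19 | 0.06 | 0.004 |

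**The case against.** The best defence is that this is a slip of wording. The statistic is called dose-normalised three times, the limits are centred on 1, and the defining clause can be read as saying only which two doses are compared. An experienced programmer would probably use the right formula. A value near 3 or 4 beside a slope near 1, with the log-log plot that 6.3.3 also requires, should be noticed. That the intent is clear stands. It does not make the written definition correct: the clause is the only one that defines the statistic, and a programmer who uses the right formula departs from it.

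A second point also stands. By symmetry, the flat-exposure probabilities above equal the chance that the dose-normalised rule declares a truly proportional drug. In Part 1 at CV 30–40% that chance is only about 5% to 0.1%, so both versions would usually fail to declare and the yes/no outcome would often agree. The declaration changes materially only at low CV. The reported estimate, however, is wrong at any CV.

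Third, flat exposure is hypothetical. The dose rationale in protocol 6.3.3 assumes the same clearance at each dose, which implies β = 1. That is also the case in which the rule as written does worst.

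Finally, little rests on R_dnm. It is not a listed PK endpoint in SAP 3.1.2, no escalation decision uses it, and β is estimated correctly either way. This limits the severity.

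**Conclusion.** The definition is wrong as written. Followed literally, it returns about 4 (Part 1) or 3 (Part 2) for an exactly proportional drug against limits of 0.8–1.25, and in effect never declares proportionality. The values 4 and 3 rest on the planned doses and shift if lower doses were given, but R as defined equals r at β = 1, which exceeds 1.25 for every dose range considered here. The interval widths and probabilities rest on an assumed CV; the algebra does not.

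The point should be fixed, but it does not threaten the trial. The exposure is to a wrong estimate or a wrong proportionality statement in the report, recoverable from the fitted slope. Whether a Part 1 result has already been produced, and with which formula, cannot be told from the documents.

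**What to change.** Replace the defining clause in SAP 6.3.3 with:

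R_dnm = [predicted GM at highest dose / highest dose] ÷ [predicted GM at lowest dose / lowest dose] = (highest dose / lowest dose)^(β−1), with its 90% CI obtained by putting the 90% confidence limits of β into the same expression.

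Add that highest and lowest mean the doses actually given within each part. Then confirm that any Part 1 dose-proportionality result already produced used this formula, and recompute it from the slope if not.

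The cost is one clause and one program check. Data, model and limits stay as they are.

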6.4. Pharmacodynamic Analysis

PD analysis will be performed using the PD population. Additional COVID-19 subgroup analysis for those being impacted by COVID-19 versus those not being impacted may be provided for PD endpoints using the descriptive statistical summary table and/or inferential statistics, if deemed necessary.

6.4.1. Analysis of Exploratory Incretins/Metabolic Hormone Endpoints

The observed values and the change from baseline in incretins/metabolic hormone endpoints, such as GLP-1, GIP, glucagon, FGF21 and leptin, will be summarized descriptively by cohort/dose level and time point.

A mixed model repeated measures analysis will be performed with the change from baseline in incretins/metabolic hormone endpoint as the dependent variable, treatment group, analysis visit and the interaction between treatment group and analysis visit as factors, and the baseline of the dependent variable as a covariate. Repeated measures on each subject, at each visit, will assume an unstructured covariance structure. If the model fails to converge, other covariance structures will be considered and selected based on model fit as determined by Akaike information criterion.

The least squares (LS) mean, standard error of LS mean and 95% confidence interval will be presented by treatment group for each post baseline analysis visit. The LS mean difference between active treatment group minus pooled placebo, standard error of the LS mean difference from placebo, and the 95% confidence interval will be presented by analysis visit.

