6.4. Subjects Identification and Randomization

6.4.1. Screening No.

The unique subject identification (SID) number will be assigned to all screened subjects. The SID number consists of 4 digits and is numbered sequentially from X001 (X is institution's number.). The SID number is given in the order of subject screening (according to order consent of participation when the screening conducts in the same day.). The SID number would be managed from screening to randomization. The subject who has been withdrawn from this study prior to randomization and after screening will retain their SID number.

6.4.2. Randomization No.

The subjects enrolled in this study would be assigned randomly to each treatment group. The randomization code will be generated by biostatistics staff who are not related to this study, (independent to this study), using statistic software (SAS®, latest version) and block randomization method considering the predefined block size. Subjects in Part 1 will be assigned to HM15136 and placebo in a 3:1 ratio, in the case of Part 2, up to 66 subjects will be assigned to HM15136 and placebo. Thirty (30) subjects in Cohort 4 will be assigned in a ratio of 1:1 and 12 subjects in each Cohort 5-7 will be in a 3:1 ratio according to rules below in Table 1.

After the signing of informed consent, the investigator assigns the randomization number in the order of subjects who meet the in/exclusion criteria and are selected for participation. According to the protocol, the randomization number is given on Day -1 or Day -2, prior to administration of IP. The randomization number is kept in a limited place accessible only by pharmacy staff and can only be accessed by other personnel if the blind is broken. The randomization number includes the 3 digits of subject's number as presented in the below table.

Table 1. Randomization No. and Treatment Assignment

Part	Cohort	Randomization No.	Treatment Assignment*	
Part 1	1	101 - 112	HM15136 0.02 mg/kg (N=9)	Placebo (N=3)
	2	201 - 212	HM15136 0.04 mg/kg (N=9)	Placebo (N=3)
	3	301 - 312	HM15136 ≤0.08 mg/kg (N=9)	Placebo (N=3)
Part 2	4	401 - 430	HM15136 0.06 mg/kg (N=15)	Placebo (N=15)
	5	501 - 512	HM15136 ≤0.02 mg/kg (N=9)	Placebo (N=3)
	6	601 - 612	HM15136 ≤0.04 mg/kg (N=9)	Placebo (N=3)
	7	701 - 712	HM15136 ≤0.06 mg/kg (N=9)	Placebo (N=3)

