10.2.3. Restrictions**1) Restriction on food and beverages**

The subjects should fast without taking any food or drink (except water) for at least 10 hours before in-house periods, OPD visits, or follow-up visits.

During the in-house periods, a standardized weight maintaining diet will be served to the subjects. Subjects should maintain their normal diet after discharge and until the end of the study.

Therefore, the investigator or the staffs involved in the study should educate the subjects in relation to the above items during in-house and OPD visits and check whether the subject complied by checking the diet diaries.

Food intake is not allowed within 10 hours before the IP administration and 4 hours after IP administration on Day 1 and 78. This question should be recorded by asking the subjects before the IP administration.

During In-house periods 1 and 2, meals are served. For details please see the Operations Manual. On Day 1 and 78 (the days of IP administration), breakfast is not served to subject and lunch is served after 4 hours of evaluation/collection.

Breakfast is served after collecting fasting state samples.

Foods with grapefruit, pomelo, or seville Orange (including marmalade) or beverages are not allowed within 48 hours before, or during the in-house periods.

Products containing quinine (e.g., carbonated water) are not allowed within 7 days before, or during the in-house periods.

Per COVID-19 modification, standardized meals might not be available and subjects may therefore be provided with a snack bag.

2) Contraception

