2.3. Sample Size and Power

This study determined the number of subjects without consideration of statistical validity. The number of subjects for the Part 1 will be 12 (HM15136: placebo = 9:3) for each cohort, and for the Part 2 will be up to 66, 30 for Cohort 4 (HM15136: placebo = 15:15) and 12 for Cohorts 5-7 (HM15136: placebo = 9:3). This is consistent with the typical sample size used in the similar study to evaluate safety and PK. Therefore, no formal sample size calculation will be performed. Note that the conduct of Cohorts 6 and 7 will be optional. Safety and tolerability of the study drug will be assessed based on adverse events, laboratory parameters, physical examination, vital signs, and ECG parameters throughout the duration of the study. Safety analysis will involve examination of the descriptive statistics and individual subject listings for any effects of study treatment on clinical tolerability and safety.

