6.1. General Considerations

Summary and analysis of Part 1 and Part 2 will be separate. Placebo subjects within each part of the study will be pooled in summaries and listings. Exploratory analysis for subgroup of subjects being impacted by COVID-19, versus those not being impacted, may be conducted to assess missing data due to COVID-19. As the number of subjects in the subgroup analysis will be much smaller than the original planned population, caution should be taken when interpreting the inferential statistical results. Please refer to Sections 6.3 and 6.4 for COVID-19 subgroup analyses.

All data collected in the EDC and external data sets will be listed using the safety population.

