6.4.6. Analysis of Exploratory MRI Endpoints

Observed values and the change from baseline (absolute) and percent change from baseline (relative) in MRI endpoints such as of liver fat via MRI-PDFF and visceral fat volume, will be summarized descriptively by cohort/dose level and time point. **Note:** MRI-PDFF at Day 85 is only measured if the Day -1 or Baseline visit is $\geq 10\%$ liver fat.

A Wilcoxon Mann Whitney test will be performed to test the change from baseline and the percent change from baseline in MRI endpoints by treatment group. The p-value from the Wilcoxon Mann Whitney test will be presented. In addition, the estimate of the median and the exact 95% confidence limits estimated by the Hodges-Lehmann estimator will be presented.

In addition, an analysis of variance (ANOVA) model will be performed; the difference between each HM15136 dose group and placebo and its associated 95% confidence interval and p-value will be presented.

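### Part 2 pharmacodynamic contrasts use placebo pooled over separately randomised cohorts with no cohort term, so the contrast for a 9:3 cohort is mostly non-randomised

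*SAP*

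**What the plan says.** SAP 6.1 states that "Summary and analysis of Part 1 and Part 2 will be separate" and that "Placebo subjects within each part of the study will be pooled in summaries and listings". Protocol 11.2.1 also combines placebo across cohorts.

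SAP 6.4.1 specifies a repeated-measures mixed model with "treatment group, analysis visit and the interaction between treatment group and analysis visit as factors, and the baseline of the dependent variable as a covariate". The reported contrast is the "LS mean difference between active treatment group minus pooled placebo", with a standard error and 95% confidence interval by visit. Sections 6.4.2, 6.4.4, 6.4.5 and 6.4.7 to 6.4.9 call for a similar model. For MRI endpoints, section 6.4.6 plans a Wilcoxon test and an ANOVA, from which "the difference between each HM15136 dose group and placebo and its associated 95% confidence interval and p-value will be presented".

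Randomisation is by cohort. Protocol 6.4.2 gives each cohort its own number series and states that "Thirty (30) subjects in Cohort 4 will be assigned in a ratio of 1:1 and 12 subjects in each Cohort 5-7" are assigned 3:1. SAP 2.3 gives the sizes as "30 for Cohort 4 (HM15136: placebo = 15:15) and 12 for Cohorts 5-7 (HM15136: placebo = 9:3"). Cohorts 6 and 7 are optional, and SAP 2.1 allows Cohort 4 to run with fewer subjects.

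Neither document plans a cohort term, a cohort-stratified analysis, a check that placebo groups agree, or an own-cohort comparison. The nearest item is an optional comparison of subjects affected and not affected by COVID-19 (SAP 6.1 and 6.4).

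**The concern.** Each cohort carries one dose, and randomisation protects only the comparison of that dose with placebo subjects in the same cohort. The planned contrast sets the dose group against placebo subjects drawn mainly from other cohorts. Under no drug effect it is centred on zero only if the cohorts would have changed alike over 12 weeks. The baseline covariate adjusts for different starting values. It does not adjust for different change caused by calendar time, setting or diet.

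The documents give reasons why such differences are possible. Protocol 6.2 and 6.3.4 place the decision to open Cohort 6 after all 12 Cohort 5 subjects have reached Day 113, so the later cohorts are separated in time by design. In-house periods provide a standardised weight-maintaining diet, but under the COVID-19 modification "standardized meals might not be available and subjects may therefore be provided with a snack bag". The same modification moves some fasting glucose readings from the clinic to a home glucometer. Weight, glucose and lipids could respond to any of these. A cohort difference would then be read as an effect of the lower doses in type 2 diabetes, or would mask one.

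**Working it through.** **Inputs.** Part 2 arm sizes are from SAP 2.3. The two-sided 0.05 level and the absence of multiplicity adjustment are from SAP 6.1.1. The documents give no SD, effect size or cohort difference, so results are in units of the residual SD, and the cohort shift d is assumed.

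**Plan's own figure.** 30 + 3 × 12 = 66 Part 2 subjects, as stated.

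**Share of Cohort 5's comparator from other cohorts** = 1 − 3 / (all Part 2 placebo).

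| Cohorts run | Cohort 4 placebo = 15 (planned) | Cohort 4 placebo = 6 (assumed) |
|---|---|---|
| 4-5 | 15/18 = 83% | 6/9 = 67% |
| 4-6 | 18/21 = 86% | 9/12 = 75% |
| 4-7 | 21/24 = 88% | 12/15 = 80% |

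Cohort 6, if run, has the same shares as Cohort 5 in the last two rows.

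**Bias.** With no drug effect and Cohort 5 shifted by d from the other cohorts, the expected difference is share × d. That is 0.83d to 0.88d at planned numbers.

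**How often a 95% interval excludes zero with no drug effect** (single-visit linear-model simulation, Cohorts 4 and 5 only):

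| d (SD) | Cohort 4 at 15:15 | Cohort 4 at 6:6 |
|---|---|---|
| 0 | 5% | 5% |
| 0.25 | 8% | 6% |
| 0.5 | about 16% | about 10% |
| 1.0 | about 48% | about 24% |

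As a check on the d = 0.5 row, the non-central t gives 16.9% and 10.4%. With a cohort term in the single-visit model at 15:15, the rate stays at about 5% for every d.

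**Precision of the within-cohort contrast**, SE = √(1/n active + 1/n placebo):

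- A 9:3 cohort: within √(1/9 + 1/3) = 0.667; pooled √(1/9 + 1/18) = 0.408. The ratio is 1.63.
- The difference detectable with 80% power for such a cohort rises from (1.96 + 0.84) × 0.408 = 1.14 SD to 1.87 SD.
- Cohort 4 at 15:15: within √(2/15) = 0.365; pooled 0.350 (18 placebo) to 0.329 (24 placebo). The cost is 4% to 11%.
- Cohort 4 at 6:6: within √(2/6) = 0.577; pooled 0.527 (9 placebo) to 0.483 (15 placebo). The cost is 10% to 20%.

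**Which cohort term is needed.** The model is repeated-measures, and the worry is a difference that develops over time. A generalised least squares check used 15:15 and 9:3 arms, 4 or 8 visits, compound symmetry with correlation 0.5 or 0.7, and a cohort shift growing linearly to d at the last visit. Last-visit bias is 0.83d as planned, 0.31d to 0.37d with a cohort main effect only, and 0 with cohort-by-visit.

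**The case against.** Pooling placebo is a deliberate, prespecified choice in both documents. It is reasonable with three placebo subjects per cohort, and the precision gain is real. PD is exploratory, the sample size was set without a formal calculation, and dose decisions rest on safety review, not on these contrasts. All of that stands. It limits the severity and argues for keeping the pooled result.

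Four stronger readings are tempting and are not supported.

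- A reader might take 83-88% as fixed. It needs 15 Cohort 4 placebo subjects, and the current text allows fewer. No final number is given.
- A reader might infer that Cohort 4 ran in-house and Cohort 5 ran as outpatients. SAP 6.1.3 says that all Part 2 subjects might follow the modified schedule, and SAP 2.1 lets Cohort 5 overlap Cohort 4. Both narrow the gap between these two cohorts. Neither removes it, and neither helps the later Cohorts 6 and 7. The SAP 6.1.3 sentence also names two Cohort 4 subjects alongside all of Part 2, to which Cohort 4 belongs, so it does not settle who followed which schedule.
- A reader might describe these contrasts as significance tests throughout. Section 6.4.1 lists intervals, not p-values. Explicit p-values for a treatment comparison appear in section 6.4.6. Elsewhere the general 0.05 rule and an interval excluding zero are the only basis.
- A reader might conclude that error rates are inflated. That depends on d, for which the documents give no value.

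The optional COVID-19 subgroup analysis addresses one possible cause of a cohort difference. It does not restore a within-cohort comparison.

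**Conclusion.** The structural point holds. In Part 2, the planned PD contrast for a 9:3 cohort rests mostly on placebo subjects who were not randomised with that dose group, and no planned analysis shows whether this matters. The share is 83-88% at planned numbers and lower if Cohort 4 stayed small. The 16% and 10% figures illustrate an assumed 0.5 SD shift and do not predict what will occur.

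Severity is minor to moderate. The endpoints are exploratory, but the remedy is cheap, and for Cohort 4 a properly randomised contrast is available at little loss of precision. Part 1 has the same structure (6/9 = 67% for every cohort), but SAP section 1 places this amendment after the Part 1 database lock, so the change is aimed at Part 2.

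**What to change.** Amend the SAP before Part 2 unblinding:

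- **6.4.1 and the sections that reuse it:** keep the pooled contrast. Add a supportive model with cohort and cohort-by-visit as fixed factors, so that each dose is also compared with its own cohort's placebo at each visit. A cohort main effect alone is not enough.
- **6.4.6:** add cohort to the single-visit ANOVA, and add a cohort-stratified Wilcoxon test.
- **Treatment group:** define it by cohort, so that Cohorts 4 and 7 are not merged if they share a dose.
- **Cohort 4 (1:1):** report the within-cohort contrast as the main one.
- **9:3 cohorts:** print the within-cohort estimate and interval beside the pooled one, as a check on direction only. At 0.667 against 0.408 SD it cannot confirm or refute the pooled result. Footnote that the pooled contrast uses placebo subjects from other cohorts and is not a fully randomised comparison.

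The cost is SAP wording and one extra model run per endpoint, with no new data. For Cohort 4 the SE rises by about 4-11% at 15:15, depending on how many later cohorts run, and by about 10-20% at 6:6.
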